#### *7.10.3 Laboratory*

##### Microbiology assessments

- Fungal KOH / saline microscopic assessment performed? (Yes/No)
- Presence of hyphae? (Present/Absent)
- VVC diagnosis (Present/Absent)
- Vaginal swab taken for culture? (Yes/No)
- Vaginal swab culture result (Positive/Negative)
  - If positive, species found should be indicated (4 categories + other)
- Vaginal swab taken for sequencing? (Yes/No) If No, specify reason (text)

##### Gynecological examination:

- Gynecological examination performed? (Yes/No)
- Vaginal pH (see [Section 7.10.1](#) above)

The categorical microbiology laboratory parameters, as specified above, will be summarized in frequency tables by visit.

#### *7.10.4 Physical examination*

Not applicable.

#### *7.10.5 Vital signs*

Not applicable.

#### *7.10.6 Electrocardiogram*

Not applicable.

### ***7.11 Changes to planned analysis***

In addition to what is stated in the CIP, a sensitivity analysis is added in the analysis of the primary clinical performance endpoint. In this, patients responding "Negative" to the eCRF variable "Vaginal swab culture result", see [Section 7.10.3](#) below, will be excluded.

In the CIP, one Per-protocol analysis set was defined. In addition to this a second Per-protocol analysis set will be defined with the purpose of analysing recurrence, see [Section 7.2.2](#) above. The rationale for this is that the different recurrence rate analyses are regarded as important to also perform using a

“per protocol” approach. The main purpose with this per protocol dataset is thus to analyse Recurrence.

A clarification regarding the secondary endpoint

- Proportion of patients receiving prolonged treatment

is made. This endpoint is obviously intended to be based on “All patients”. However, in the CIP, this endpoint was unintentionally listed under the heading “For patients receiving prolonged treatment”. In this document it has therefore been listed in the correct heading “All patients”.

A subgroup analysis, based on whether the patients at Day 0 reported 3 or more Vaginal Candida infections during the last 12 months or not, has been added for the primary clinical performance endpoint, see [Section 7.1.8](#) above.

## 8 Derived variables

---

### 8.1 Disposition of patients

A screening failure is defined as a screened but not enrolled patient. An enrolled patient is defined as having passed the screening procedures and given informed consent. An enrolled patient who has received at least 1 dose of study treatment is qualified to be included in FAS.

### 8.2 Demographics and baseline characteristics

#### 8.2.1 Age

Age will be computed as the integer part of the time in years between the date of birth and the date the written informed consent was signed, using the SAS function `yrdif()` with the basis parameter set to ‘age’. For patients for whom only the year of birth is collected, age will be computed as the difference between the year the informed consent was signed and the year of birth.

#### 8.3 Body mass index

Not applicable.

#### 8.4 Change from baseline

Change from baseline will be computed as the difference between a post-baseline value and the corresponding baseline value. This is applicable for the change in the CVVS score and the change in the sum of 3 vulvovaginal symptoms scores (itching, burning, and irritation), as well as for vaginal pH from Day 0 to Day 7.

#### 8.5 Clinical cure rate

Clinical cure rate is based on a binary variable, where a clinically cured patient is

- Defined as the absence of signs and symptoms of VVC in terms of having a composite vulvovaginal signs-and-symptoms (CVVS) score equal to or below 3.
  - Each of the following 6 vulvovaginal signs and symptoms will be individually scored using the scoring scale below and then added together to determine the CVVS score.
    - Vulvovaginal signs: erythema, edema, or excoriation
    - Vulvovaginal symptoms: itching, burning, or irritation
  - Scoring Scale: each score should be objectively defined.
    - 0 = none (absent)
    - 1 = mild (slight)
    - 2 = moderate (definitely present)
    - 3 = severe (marked, intense)

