1 INTRODUCTION

1.1 Indication

Vaginal infection is a huge and today largely underestimated problem, affecting between 70% to 75% of women at some point in life, and between 5% to 8% of adult women have recurrent vulvovaginal candidiasis (VVC) with ≥ 4 episodes yearly.¹ As previously described, current antifungal agents for VVC treatment and prevention are prone to resistance development and many patients relapse after treatment.² Also, oral antifungal therapies are not recommended during pregnancy due to the potential risk of fetal harm and spontaneous abortions.^{3,4} Therefore, treatment guidelines recommend that topical, rather than oral, antifungal therapy is used in pregnant women.⁵

The vaginal microbiome is a dynamic system with a complex mixture of microorganisms in different ratios and quantities, which depend on lactic-acid producing bacteria to maintain a weakly acidic environment, see overview.⁶ Changes to vaginal microflora will increase the pH, thereby forming a favorable environment for vaginal pathogens. Vaginal or systemic antibiotics treatment is frequently followed by VVC, likely due to the elimination of the protective bacterial flora, thereby allowing *Candida* overgrowth.⁷⁻¹¹ Infections are also facilitated due to the mucosal effect of increased estrogen levels and a weakened immune system during pregnancy.¹² Recurrences are more common in pregnant women, and their therapeutic response is reduced compared to non-pregnant women.^{13,14} Further, contraceptive pills, menstruation, and diabetes mellitus have been identified as predisposing factors for VVC.^{15,16} *Candida albicans* is the most prevalent pathogen, which has been reported in epidemiological studies as represented in between 85% and 95% of vaginal isolations.¹⁷⁻¹⁹ *Candida glabrata* is the second most prevalent pathogen.²⁰

Many women diagnose themselves with VVC and purchase over-the-counter (OTC) antimycotics for treatment. However, many misdiagnose themselves, leading to unnecessary or inappropriate treatment;²¹ Ferris and colleagues found that only 34% of women who purchased OTC antimycotics for VVC did, in fact, have VVC.²²

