4.2 Inclusion Criteria

Inclusion and exclusion criteria in the fungal study should follow the FDA Vulvovaginal signs-and-symptoms score:

- Adult, post-menarchal, pre-menopausal women aged 18 years or older
- Diagnosis of VVC, defined as having a white or creamy vaginal discharge plus the following findings:
 - *At least* 2 of the following signs and symptoms of VVC that are characterized as *at least* moderate: itching, burning, irritation, edema, redness, or excoriation.
 - Potassium hydroxide (KOH) or saline preparation from the inflamed vaginal mucosa or secretions revealing yeast forms (hyphae or pseudohyphae) or budding yeasts.
- Having decisional capacity and providing written informed consent.
- Negative urine pregnancy test at screening.
- Refrain from using any intravaginal products (i.e., contraceptive creams, gels, foams, sponges, lubricants, or tampons, etc.) during the study period.
- Refrain from sexual intercourse or use a condom until Day 7
- Signed informed consent and willing and able to comply with all study requirements.

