5.7 Prior and Concomitant Medication

Information about any concomitant medication, including OTC medications and vitamins taken by patients during the study and within 14 days prior to inclusion shall be documented in the eCRF. The generic name or trade name, dosage, and reason for use shall be recorded for all medications.

NOTE: Antifungal medication during the study and within 14 days prior to inclusion is strictly prohibited

See [Appendix 1, Section 3](#) for specific questions.

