### 7.2.1 *Full analysis set*

Full Analysis Set (FAS): This is the primary population and comprises all patients entering the study and having received at least 1 dose of study treatment. Analyses of clinical performance will be performed against this population.

In addition to this, two sub-populations based on this FAS will be formed: “FAS (For patients not receiving prolonged treatment)”, and “FAS (For patients receiving prolonged treatment)”.

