### 7.9.1 Primary endpoints

- Clinical performance endpoint: Clinical cure rate on Day 7 will be calculated and presented together with a one-sided 95 % confidence interval based on the exact binomial distribution (Clopper-Pearson).
- Clinical safety endpoint: Safety and tolerability will be assessed according to [Section 7.10.2](#).

The primary clinical performance endpoint is the Clinical cure rate on Day 7, where clinical cure is defined as the absence of signs and symptoms of VVC in terms of having a composite vulvovaginal signs-and-symptoms (CVVS) score equal to or below 3, see [Section 3.1.1](#) above. The primary performance objective of the trial is to show that the Clinical cure rate is above 40 %, *i.e.* to show that the lower limit of the one-sided 95 % CI for the observed cure rate is above 40 %.

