### **8.10 Proportion of patients receiving rescue treatment on Day 14**

The proportion of patients receiving rescue treatment (fluconazole, as defined in the CIP) on Day 14 is based on a binary variable which indicate whether a patient has used rescue treatment or not, i.e. as shown by collected CRF concomitant medication data, where start date of the rescue medication should be from or after Day 14. Start and stop date of use of such rescue medication will be presented in data listings.

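### Day 7 cure is judged on the CVVS score alone, so a patient who took a prohibited antifungal before the visit still counts as a pessary cure

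*SAP*

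**What the plan says.** SAP 8.5 defines a clinically cured patient by the score: "Defined as the absence of signs and symptoms of VVC in terms of having a composite vulvovaginal signs-and-symptoms (CVVS) score equal to or below 3". SAP 7.9.1 and Protocol 2.1 and 6.1 use the same criterion, and none of them adds a condition on other treatment. The primary analysis set "comprises all patients entering the study and having received at least 1 dose of study treatment" (SAP 7.2.1). SAP 7.1.5 analyses the data as observed, without imputation. The performance objective in SAP 7.9.1 is "to show that the lower limit of the one-sided 95 % CI for the observed cure rate is above 40" per cent, using the exact Clopper-Pearson limit.

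Protocol 5.7 states: "Antifungal medication during the study and within 14 days prior to inclusion is strictly prohibited". This is a rule of conduct. Neither document gives it a consequence for the cure variable.

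Two other analyses touch the primary endpoint:

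- **Per-protocol (SAP 7.2.2 and 7.9).** Major deviations are to be defined at the clean file meeting, and antifungal use is not named. The analysis is produced only if the number of exclusions is judged relevant, and its role is supportive.
- **Sensitivity analysis (SAP 7.9.4).** This removes culture-negative patients only.

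**The concern.** The trial has one arm, so nothing balances the effect of outside treatment. A patient with persistent symptoms who starts an antifungal on, say, Day 4 and scores 2 on Day 7 enters the numerator of the rate tested against 40%. If the antifungal produced that score, the pessary is credited with a cure it did not achieve.

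There are two routes by which this could happen before Day 7. One is self-treatment against the protocol. The other is fluconazole given at early withdrawal, which Protocol 5.2.1 allows at any point, if a full CVVS score is still recorded afterwards. The planned Day 14 prescription is not a route, because it follows both the Day 7 assessment and the Day 14 examination.

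The same definition governs the Day 14 cure rate in patients on prolonged treatment (SAP 7.9.2, endpoint viii), where the period at risk is longer.

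**Working it through.** **Inputs.** Null rate 40%, assumed true rate 70%, one-sided 95% limit, 22 patients needed and 24 planned (SAP 5.1, 7.9.1). Antifungal effectiveness of 85% and 35% is taken from the short-term clinical cure rates quoted in Protocol 1.1, with 100% as the extreme. The documents give no rate of antifungal use during the study, so 5%, 10% and 15% are assumptions.

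**The plan's own figure.** The normal approximation gives n = [(1.645·√(0.4·0.6) + 1.282·√(0.7·0.3)) / 0.3]² = 21.56, rounded up to 22. The stated figure is reproduced. With the exact limit that will actually be used, power is 81.4% at 22 patients (14 cures needed) and 84.7% at 24 (15 cures needed). That is a separate matter. What counts here is the boundary of 15.

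**The boundary.** The Clopper-Pearson one-sided lower limit for x cures in n is the 5% quantile of Beta(x, n − x + 1).

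| Handling of one antifungal-assisted cure | Result | Lower limit | Above 40%? |
|---|---|---|---|
| Counted as cured (current rule) | 15/24 | 43.7% | yes |
| Dropped (per-protocol) | 14/23 | 41.7% | yes |
| Counted as not cured | 14/24 | 39.7% | no |

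Dropping her and counting her as not cured lead to opposite conclusions, so the per-protocol set does not replace a rule in the endpoint.

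**Effect on the chance of false success.** Let the pessary-only rate be 0.40. Let q be the share of otherwise uncured patients who use an antifungal before Day 7, and e the probability that it brings such a patient to 3 or less. The apparent rate is p = 0.40 + 0.60·q·e, and the chance of success is P(X ≥ 15) for X ~ Binomial(24, p). For example, q = 0.10 and e = 1 give p = 0.46 and 7.8%.

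| q | e = 100% | e = 85% | e = 35% |
|---|---|---|---|
| 0 | 2.2% | 2.2% | 2.2% |
| 5% | 4.3% | 3.9% | 2.8% |
| 10% | 7.8% | 6.6% | 3.5% |
| 15% | 13.2% | 10.5% | 4.4% |

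On average 0.60 × 24 = 14.4 patients are otherwise uncured, so these values of q correspond to about 0.7, 1.4 and 2.2 patients.

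**Where the nominal 5% is passed.** P(X ≥ 15) reaches 5% at p = 0.4371, the lower limit for 15/24. Solving q = 0.0371 / (0.60·e) gives 6.2%, 7.3% and 17.7% for e = 100%, 85% and 35%.

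**The case against.** Three parts of the opposing case stand.

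- **Use may be zero.** Protocol 1.1 says "Many women diagnose themselves with VVC and purchase over-the-counter (OTC) antimycotics for treatment", but this describes women who self-diagnose. It does not describe examined patients already on treatment and told not to use antifungals. It makes the behaviour plausible and gives no rate for this trial.
- **The size depends on effectiveness.** At 35%, usage up to 15% keeps false success below 5%. The 7.8% and 13.2% figures require every otherwise uncured user to be cured by the antifungal, so they are upper bounds.
- **The plan is not blind to such use.** New medication is asked about on Day 4 and Day 7, and coded and tabulated under SAP 7.7. A breach would be listed as a deviation and could lead to per-protocol exclusion. Protocol 9 and 9.1 also allow measures against bias and sensitivity analyses. All of this is discretionary or descriptive, however, and none of it changes how the patient is scored in the primary analysis.

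The withdrawal route is also narrow. A withdrawn patient reached only by telephone has no scored signs, so her CVVS is missing and she does not meet the cure definition.

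A reader might infer three stronger points that the documents do not support:

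- **That SAP 8.10 hides early antifungal use** because "start date of the rescue medication should be from or after Day 14". That variable serves an endpoint defined at Day 14, and SAP 7.7 identifies rescue fluconazole without a Day 14 limit.
- **That symptom-relieving drugs need the same treatment.** Oral antihistamines, oral analgesics and external vulvar creams are not prohibited. Protocol 4.2 asks patients to "Refrain from using any intravaginal products (i.e., contraceptive creams, gels, foams, sponges, lubricants, or tampons, etc.) during the study period", which concerns intravaginal products. Failing every patient who took an analgesic would misclassify those who took it for an unrelated reason, and the documents offer no basis for a look-back period.
- **That the error always favours success.** A user whom the pessary would have cured anyway adds no inflation. Protocol 1.3.2 names local irritation as the most frequent adverse event of topical azoles, and irritation could raise a score.

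**Conclusion.** The point holds as a gap in the endpoint definition. Applied as written, the cure rule credits the pessary with the outcome of a patient who took a prohibited antifungal before the Day 7 assessment, and no mandatory analysis corrects this. One such cure at 15 of 24 is the difference between a lower limit of 43.7% and one of 39.7%.

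The effect on the false-success rate is conditional. It rests on a pessary-only rate of exactly 40%, on an assumed usage rate, and on effectiveness between 35% and 100%. Over 5% to 15% use, it runs from 2.8% to 13.2%, against 2.2% with no use. The documents do not show that any such use will occur, and these figures should not be read as a forecast of the error rate. The case for a rule is that handling alone can decide the conclusion, so it should be fixed before the data are seen.

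**What to change.** Add to SAP 8.5, with a matching line in SAP 7.9.1: a patient who starts any antifungal other than the study pessary, topical or systemic, after the first pessary and before the Day 7 assessment is counted as not cured on Day 7, whatever her CVVS score. Apply the same rule up to the Day 14 assessment for endpoint viii. Identify use from the coded concomitant medication in SAP 7.7, by start date.

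The change needs a few lines of SAP text and minor programming. The medication data are already collected, and no visit or treatment rule changes.

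The statistical cost is that a user whom the pessary would have cured anyway becomes a failure, so the cure rate can only stay the same or fall. If users were a random 5% of all patients at a true pessary rate of 70%, the expected rate would be 0.70 × 0.95 = 66.5%, and exact power at 24 patients would fall from 84.7% to 74.0%. If all users came from patients the pessary would not cure, no power would be lost. If nobody uses an antifungal, the primary result is unchanged.

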### ***8.6 Proportion of patients having a reduction in the CVVS score***

The proportion of patients having a reduction in CVVS score compared to Day 0 is based on a change from baseline variable, see [Section 8.4](#) above, where a patient with reduction is defined as when the change from baseline in the CVVS score is  $< 0$ . In case of one or more missing value(s) among the 6 items included in the calculation of the CVVS score, the CVVS score will remain missing.

### ***8.7 Proportion of patients having a reduction in the sum of the 3 vulvovaginal symptoms scores***

The proportion of patients having a reduction in the sum of the 3 vulvovaginal symptoms scores (itching, burning, and irritation) compared to Day 0 is based on a change from baseline variable, see [Section 8.4](#) above, where a patient with reduction is defined as when the change from baseline in the sum of the 3 vulvovaginal symptoms scores is  $< 0$ . In case of one or more missing symptom value(s) in the 3 vulvovaginal symptom items (itching, burning, and irritation), the sum of the 3 vulvovaginal symptoms scores will be set to missing.

### ***8.8 Recurrence rate***

Recurrence rate is based on a binary variable, where a recurred patient is defined as a patient clinically cured on Day 7 and thereafter responding “yes” at specified follow-up visits to a yes/no question from the patient questionnaire on whether the symptoms have recurred.

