3.5.5 Day 7 (+2 Days); Follow-up Visit

Patients will visit the clinic on Day 7 to have gynecological examination performed. The Investigator or an authorized designee will assess the presence of vulvovaginal signs (erythema, edema, or excoriation) and symptoms (itching, burning, or irritation) and score each sign and symptom.

Vaginal samples will be examined by microscope to reveal yeast forms (hyphae or pseudohyphae) or budding yeast and secretion samples collected by swab to be used for sequencing analysis of the vaginal microbiome. Vaginal pH will also be assessed.

If VVC symptoms are still present, patients will have prolonged treatment and receive additional doses of investigational product to be administered at home on Day(s) 7, 9, 11, and 13.

In addition, patients will be asked questions from the patient questionnaire to assess: usability; concomitant medications; and AEs, if any.

Procedures performed:

- Gynecological examination by Investigator or authorized designee evaluating signs (erythema, edema, or excoriation) and symptoms (itching, burning, or irritation of VVC according to the scoring scale
- Fungal KOH microscope assessment
- Vaginal swab for sequencing
- Vaginal pH
- Recording of:
 - concomitant medications,
 - adverse events, and
 - usability
- Treatment dispensing and self-administration by patients if receiving prolonged treatment

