## Figure 1 Study Flow Chart

VVS = Vulvovaginal Symptoms, VS = Vaginal Swab, CVVS = Composite Vulvovaginal Signs and Symptoms

**Patients not receiving prolonged treatment** applies to patients cured at Day 7. If not cured, the flow chart **patients receiving prolonged treatment** applies. Patients will here receive fluconazole if not cured at Day 14. Adverse events will be assessed throughout the study

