### **7.1.1 Presentation of results**

If applicable, results will be presented together with the unit.

Continuous data will be summarised using descriptive statistics, and the following parameters will be reported:

- number of patients with evaluable observations and missing observations
- arithmetic mean and standard deviation
- median
- first and third quartiles
- minimum and maximum.

Categorical data will be presented using absolute frequency and percentage. When the absolute frequency is zero, the percentage will not be presented. Unless stated otherwise, the denominator for percentage calculations will be the total number of patients in the applicable analysis set, including patients with missing data. For variables with missing values, the number and percentage of patients with missing values will be presented.

Statistical testing will be performed using an overall significance level of 5%. The primary endpoint analysis will be based on one-sided testing, whereas the secondary endpoints analyses will be based on two-sided testing. Corresponding confidence intervals will be presented. See [Section 7.9](#) below for further information.

Data will be presented using an appropriate number of decimal places, to ensure that undue precision is not implied (e.g. the number of decimals should not exceed the accuracy of the measuring instrument). Raw data will be presented with the same number of decimals as collected, and derived data with an appropriate number of decimals based on general practice, mathematical rationale or scientific rationale.

Minimum and maximum values will be presented with the same number of decimals as the analysed variable and the other descriptive statistics will be presented with one decimal more. Percentages and proportions will be presented with one decimal. Confidence interval bounds will be presented with the same number of decimals as the corresponding point estimate, and p-values will be presented with 4 decimals or as '<.0001'.

Mock tables and graphs are presented in the Data Display Plan (DDP), which is a supplementary document to this analysis plan. Individual patient data listings will be presented according to the ICH E3 guideline for Structure and Content of Clinical Study Reports (2), unless stated otherwise.

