#### Hypothesis for the continuous secondary clinical performance endpoint "Change in the CVVS score"

Null hypothesis: Change from baseline is = 0.

Alternative hypothesis (two-sided): Change from baseline  $\neq$  0.

Below follows a list of all secondary endpoints followed by information on which are binary and which are continuous. Note that, as described in [Section 3.2.1](#) above, the analyses of the secondary endpoints will be performed on 3 different patient categories. These are denoted as A, B, and C below.

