#### B. For patients not receiving prolonged treatment

- vii] Recurrence rate on Day 14 and Day 35, defined as the proportion of patients clinically cured on Day 7 and thereafter responding "yes" to a yes/no question from the patient questionnaire on whether the symptoms have recurred

The endpoint vii] constitute binary variables.

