#### C. For patients receiving prolonged treatment

- viii] Clinical cure rate on Day 14, defined as the absence of signs and symptoms of VVC in terms of having a CVVS score equal to or below 3

- ix] Proportion of patients having a reduction in CVVS score on Day 14 compared to Day 0
- x] Change in the CVVS score from Day 0 to Day 14
- xi] Proportion of patients having a reduction in the sum of the 3 vulvovaginal symptoms scores (itching, burning, and irritation) on Day 11, Day 14, Day 21, and Day 42, compared to Day 0
- xii] Change in the sum of the 3 vulvovaginal symptoms scores (itching, burning, and irritation) from Day 0 to Day 11, Day 14, Day 21, and Day 42
- xiii] Recurrence rate on Day 21, and Day 42, defined as the proportion of patients clinically cured on Day 14 and thereafter responding “yes” to a yes/no question from the patient questionnaire on whether the symptoms have recurred
- xiv] Proportion of patients receiving prescription for fluconazole on Day 14

The endpoints viii], ix], xi], xiii], and xiv] are binary variables.

The endpoints x] and xii] are considered as continuous variables.

In connection to the endpoints described above, the underlying variables listed below not constituting endpoints (denoted as “other related variables” in the CIP), will be presented descriptively.

- CVVS score (can take integer values in the interval 0-18)
- Vulvovaginal signs: erythema (can take integer values in the interval 0-3)
- Vulvovaginal signs: edema (can take integer values in the interval 0-3)
- Vulvovaginal signs: excoriation (can take integer values in the interval 0-3)
- Sum of all vulvovaginal signs score (can take integer values in the interval 0-9)
- Vulvovaginal symptoms: itching (can take integer values in the interval 0-3)
- Vulvovaginal symptoms: burning (can take integer values in the interval 0-3)
- Vulvovaginal symptoms: irritation (can take integer values in the interval 0-3)
- Sum of all vulvovaginal symptoms score (can take integer values in the interval 0-9)

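### SAP 8.8 ties every recurrence rate to Day 7 cure and names no denominator, so the Day 21/42 rate is near zero read literally and, under the SAP's default denominator, is diluted by patients never cured

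*SAP*

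**What the plan says.** The SAP's derivation section has a single rule for recurrence: "Recurrence rate is based on a binary variable, where a recurred patient is defined as a patient clinically cured on Day 7" and then answering yes at the specified follow-up contacts. It does not define a patient who has not recurred, and it names no denominator.

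The endpoint list in SAP 7.9.2 has two recurrence endpoints, on different paths and with different index visits:

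- Endpoint vii, for the non-prolonged path, where the answer counted is yes: "Recurrence rate on Day 14 and Day 35, defined as the proportion of patients clinically cured on Day 7 and thereafter responding".
- Endpoint xiii, for the prolonged path at Days 21 and 42, where the same answer is counted: "defined as the proportion of patients clinically cured on Day 14 and thereafter responding".

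Three further rules bear on the denominator. For categorical data, SAP 7.1.1 sets a default that holds where no exception is given: "the denominator for percentage calculations will be the total number of patients in the applicable analysis set, including patients with missing data". SAP 7.2.1 says that "two sub-populations based on this FAS will be formed", one for each treatment path. SAP 7.9.2 says that "the analyses of the secondary endpoints will be performed on 3 different patient categories": all patients, those without prolonged treatment and those with it. None of these sets is defined by cure status.

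**The concern.** A recurrence rate is meant to describe patients who were cured and then relapsed. A patient never cured cannot recur, so she should not enter the rate. Section 8.8 raises two problems here.

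First, its index visit is wrong for one of the two endpoints it serves. A programmer who derives the variable from 8.8 and applies it at Days 21 and 42 looks for patients cured at Day 7 within a group that was treated further because they were not.

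Second, with the index visit corrected to Day 14, the default denominator still brings in every Day 14 failure as a non-recurrence. The recurrence question is put to all prolonged-treatment patients at Days 21 and 42 (Protocol 3.5.11, 3.5.13 and Appendix 1), with no filter on cure. A patient not cured at Day 14 fails the cure condition whatever she answers. The rate therefore falls as the second course works less well, and reaches 0% if nobody is cured. The exact interval is also computed on that larger n.

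**Working it through.** The documents state no figure for recurrence, so there is none to reproduce. The check has four steps.

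**1. Index visit.** SAP 8.8 requires cure at Day 7; endpoint xiii requires cure at Day 14. The legend to the SAP flow chart says that the non-prolonged chart "applies to patients cured at Day 7. If not cured, the flow chart" for prolonged treatment is used. By design, then, the prolonged group holds patients not cured at Day 7, and the 8.8 numerator there is close to zero. It need not be exactly zero. Protocol 3.5.5 words the trigger differently: "If VVC symptoms are still present, patients will have prolonged treatment". A patient with residual symptoms and a CVVS score of 3 or less meets that wording while counting as cured. With 7 prolonged patients and a literal numerator of 0, the report would show 0/7 = 0%, with an exact upper limit of 1 − 0.025^(1/7) = 41.0%, whatever happened to patients cured at Day 14.

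**2. Size of the prolonged group.** Planned N is 24 and the assumed Day 7 cure rate is 70% (SAP 5.1). Expected prolonged patients: 24 × 0.30 = 7.2, about 7.

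**3. Denominator, with the index visit taken as Day 14.** Under the 7.1.1 default on the path subset:

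reported rate = recurred / all prolonged = (recurred / cured) × (cured / all prolonged).

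The documents give neither the Day 14 cure rate nor the recurrence risk for this product, so the counts below are assumed. Intervals are two-sided 95% Clopper-Pearson, as SAP 7.9.2 plans.

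| Prolonged | Cured Day 14 | Recurred | Over cured | Over whole path |
|---|---|---|---|---|
| 7 | 7 | 2 | 28.6% (3.7 to 71.0) | 28.6% (3.7 to 71.0) |
| 7 | 5 | 2 | 40.0% (5.3 to 85.3) | 28.6% (3.7 to 71.0) |
| 7 | 3 | 1 | 33.3% (0.8 to 90.6) | 14.3% (0.4 to 57.9) |
| 7 | 2 | 1 | 50.0% (1.3 to 98.7) | 14.3% (0.4 to 57.9) |

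The same relation in expectation, with the recurrence risk among cured patients held fixed (assumed values):

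| Risk among cured | Day 14 cure 100% | 70% | 40% | 20% |
|---|---|---|---|---|
| 13% | 13.0% | 9.1% | 5.2% | 2.6% |
| 26% | 26.0% | 18.2% | 10.4% | 5.2% |
| 50% | 50% | 35% | 20% | 10% |

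The two denominators agree only if every prolonged patient is cured at Day 14.

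**4. Non-prolonged path.** Here 8.8 and endpoint vii agree on Day 7, and the group is by design the patients cured at Day 7. SAP 8.9 assigns the path by doses actually taken, so a few others can fall in: early withdrawals, patients with a missing Day 7 CVVS score, and uncured patients who took no further pessary. Suppose 17 cured (24 × 0.70 = 16.8), 2 such others, and the remaining 24 − 19 = 5 on the prolonged path. With 3 recurrences the rate is 3/19 = 15.8% instead of 3/17 = 17.6%. With none of these exceptions there is no dilution.

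A related gap: SAP 7.1.1 keeps patients with missing data in the denominator, while SAP 7.1.5 bases the analysis on observed data. Neither says what happens to a cured patient whose recurrence question goes unanswered.

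**The case against.** The strongest reply is that no sentence says recurrence is computed over the whole path. Endpoints vii and xiii can be read as a proportion among patients who were cured, and on that reading the endpoint text is itself the exception that 7.1.1 allows. Nor does 8.8 say that a never-cured patient is coded as not recurred; she could be coded not applicable. This stands as far as it goes: the dilution is what the default rule yields, and the SAP does not state it outright. It does not remove the point, because 8.8 puts cure inside the definition of the event, the sets are path-based, and the two readings can differ by a factor of two or more. It also leaves the Day 7 against Day 14 conflict untouched.

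A reader might go further and infer that all the recurrence rates are materially diluted. The documents do not support that for Days 14 and 35, where the group is by design the cured patients.

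A reader might also infer that the diluted rate would be set against the 13% to 26% relapse range under Protocol Table 1. No such comparison is planned; that range is background on other products in severe disease.

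The consequences are also limited. Binary secondary endpoints are not tested (SAP 7.9.2). The Day 14 cure rate on the same path is endpoint viii, so with complete answers a careful reader could recover the cured-only rate, for example (1/7) / (3/7) = 1/3. With about 7 patients, either interval is very wide. All of this stands, and it keeps the point at the level of a secondary endpoint.

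Finally, the second per-protocol set in SAP 7.2.2 is meant for recurrence and might be limited to cured patients. Its criteria are left to the clean file meeting and no such limit is written, so it is only a possible mitigation.

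**Conclusion.** The point holds for the Day 21 and Day 42 rates. The firm part is an inconsistency: 8.8 uses Day 7 cure where endpoint xiii uses Day 14, and taken literally this leaves a numerator near zero. The second part follows from the default rule: with no denominator in 8.8, SAP 7.1.1 and the path-based sets count Day 14 failures as non-recurrent. The rate is then scaled down by the Day 14 cure fraction, for example 14.3% in place of 33.3% with 3 of 7 cured and 1 recurring. That size rests on about 7 prolonged patients (the planned 70% Day 7 cure rate) and on assumed cure and recurrence counts; the direction does not depend on them. On the non-prolonged path the effect is nil or small. The primary endpoint is not affected. The wording should still be corrected, since SAP 7.2.2 and 7.11 themselves call the recurrence analyses important.

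**What to change.** In SAP 8.8, and at endpoints vii and xiii in 7.9.2, state that:

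- recurrence is defined among patients clinically cured at the index visit for their path, Day 7 for vii and Day 14 for xiii;
- patients not cured at that visit are in neither the numerator nor the denominator;
- this is an exception to the default in 7.1.1.

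Report the numbers cured, answering and missing at each contact beside each rate, and say how an unanswered recurrence question is treated, so that 7.1.1 and 7.1.5 no longer pull apart. The two descriptions of who goes on to prolonged treatment (not cured in the flow chart, symptoms still present in Protocol 3.5.5) must also be reconciled, because they decide who is in each group.

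The cost is wording only; no new data are needed. The downside is fewer patients in the denominator and wider intervals, and the Day 21/42 rate will be higher than under the default whenever some patients are not cured at Day 14 and at least one cured patient recurs.
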